Medication/Supplement Intake & Changes	X*	X*	X*	X ^{**}	X*	X*	X*	X ^{**}	X*	X*	X*	X*	X*	X*	X*	X ^{**}
Adverse Events	X*	X*	X*	X ^{**}	X*	X*	X*	X ^{**}	X*	X*	X*	X*	X*	X*	X*	X ^{**}
Metabolic Body Weight ¹⁶				X ^{**}				X ^{**}				X ^{**}		X ^{**}		X ^{**}
BIODEX/Strength Testing												X ^{**}				
Handgrip Strength												X ^{**}				
SPPB												X ^{**}				
Step Test												X ^{**}				
Questionnaires ²													X ^{**}			
DEXA				X ^{**}				X ^{**}				X ^{**}				X ^{**}
MR Assessments (ATPmax/IMCL/IMAT)				X ^{**}				X ^{**}				X ^{**}				X ^{**}

Accelerometer Handout															X*	X[^]
Accelerometer Collection						X*		X[^]								
VO _{2max} Test															X*[^]	
Cardio Exercise Program	X*	X*	X*		X*	X*	X*		X*	X*	X*		X*	X*	X*	
Strength Exercise Program	X*	X*	X*		X*	X*	X*		X*	X*	X*		X*	X*	X*	
Deuterated H ₂ O administration ⁸	X*[^]		X*[^]	X*[^]	X*[^]											
400m Walk Test															X*[^]	

* = only on this visit for exercise cohort

[^] = only on this visit for ambulatory cohort

Phase V – Optional Resistance Training.

Following Phase IV of the study, to expedite complete recovery, subjects may attend three resistance exercise training sessions per week over a four-week period, for a total of 12 visits. Resistance exercise training will include weight training of all major muscle groups. Subjects will perform three sets of eight repetitions at 70-80% of their 1 RM for each exercise, which will include upper body and lower body muscle groups. During all exercise sessions, subjects must be supervised by qualified personnel with the appropriate training to identify if the subject is under any type of distress. Study assessments will also be performed during the 4-week resistance training according to the table below:

Assessment	Resistance Training (Optional)											
	Week 1			Week 2			Week 3			Week 4		
	1	2	3	4	5	6	7	8	9	10	11	12
Vital Signs	X	X	X	X	X	X	X	X	X	X	X	X
Medication/supplement intake and changes	X	X	X	X	X	X	X	X	X	X	X	X
Adverse events	X	X	X	X	X	X	X	X	X	X	X	X
Metabolic Body Weight ¹⁶			X			X			X			X
Resistance Training ¹	X	X	X	X	X	X	X	X	X	X	X	X
BIODEX/Strength Testing	X											X
Handgrip Strength						X						X
SPPB						X						X
Step Test						X						X
Questionnaires ²						X						X
Accelerometer Collection		X										

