from out bed rest and recovery study in older adults (recovery in leg lean mass over 4 weeks (n=20; mean \pm SD) = $+1.2 \pm 0.5$ kg). Sex will be explored as a biological variable, however, based on data from our previous bed rest and recovery study we do not expect a difference in rate of recovery between men and women (n=10 men $+1.1$ kg, n=10 women $+1.0$ kg lean mass recovery). The sample size will also provide 80% power to detect a significant mean difference of 0.38 AU in muscle mitochondrial OXPHOS protein expression between groups during recovery. The power calculations are based on two-sample t-tests for mean difference with unequal variance and a P-value of 0.05.

Statistical Analysis Plan

The **primary** outcomes, including leg lean mass, protein synthesis rate, and mitochondrial respiration, will be measured at 5 time points following 10 days of bed rest. 2x5 repeated-measures ANOVA will be performed on the dependent variables as a function of intervention (2 levels: EX and CON groups) and time (3 levels: 5x biopsy timepoints). We will also fit mixed models (fixed and random effects) to interrogate the longitudinal data. This will allow us to better account for the longitudinal nature of the data and to explore the influence of other potential predictors of changes in muscle mass. In particular, the relationship between change in IR, protein synthesis and mitochondrial function will be explored. Since many of these outcome variables are from biopsies, e.g., various mitochondria parameters will be correlated with one another, covariance will be explored, and we will also use the relative change measures of these as a bivariate outcome. Sex, race and ethnicity as biological variables will also be explored. Sex will be explored as a biological variable, however, based on data from our previous bed rest and recovery study we do not expect a difference in rate of recovery between men and women (n=10 men $+1.1$ kg, n=10 women $+1.0$ kg leg lean mass recovery).

Potential Risks and Benefits

Potential Benefits

Participants will likely receive no direct benefit from taking part in this research study.

Potential Risks

Blood draws and/or IV (lab samples, e.g.). There is a risk of pain, vasovagal syncope, hematomas, and/or infection at the blood draw site or IV insertion site (low risk of serious AEs).

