DEXA scan. There is a very small risk of cancer with excessive exposure to any radiation. There are also risks for unborn children associated with radiation exposure. The radiation dose from one scan is less than a chest x-ray. There are six scans in this study; the total radiation is less than 4 mrem, or less than the same average amount a person would receive over 3 days in America.

Muscle Biopsy. There is a risk of pain from the local anesthesia, and a risk of bruising, bleeding (hematoma) and infection at the site of the biopsy. In addition, there is a risk of skin irritation due to the steri-strips and dressing. Local sensory loss may occur by cutting a subcutaneous sensory nerve (<1 in 100), which is almost always temporary but occasionally can become permanent. On rare occasion (<1 in 1000) bleeding, requiring hospitalization, may occur. The procedures are well tolerated when performed properly.

Optional Adipose Tissue Biopsy. There is a risk of pain from the local anesthesia, and a risk of bruising, bleeding and infection at the site of the biopsy. In addition, there is a risk of skin irritation due to the steri-strips and dressing.

Oral Glucose Tolerance Test. There is a risk of pain, hematomas, and/or infection due to venipuncture (low risk of serious AEs). Nausea from glucose ingestion may occur.

Bidex/Strength testing/Exercise/Maximal Oxygen Consumption (VO_{2max}). There is a risk of changes to blood pressure, irregular, fast or slow heart rhythm, fainting, and in rare instances (<0.01%) heart attack, stroke, or death with exercise testing, at similar rates to exercising during daily life.

Activity/Heart Rate Monitoring. There are no risks associated with the wearing of monitors, however the armband/chest band that holds the monitor in place may be irritating to the skin for some subjects. Participants with nickel allergies may have irritation at the site of the monitor.

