Bed Rest Intervention. The 10-day bed rest intervention will result in a mild deconditioning that may increase fatigability and lower muscle strength (10-20% decrease) and mass (-3% approximately) and increased body fat mass of participants. Individuals with prolonged immobility are at risk for venous thromboembolism (VTE). There is also a risk of pressure ulcers – extrinsic pressure greater than capillary perfusion pressure (30mm/Hg) for a prolonged period of time results in ischemia to the affected tissue. Both hyperglycemia and hypoglycemia are risks for hospitalized patients with T2D and are associated with adverse health outcomes. However, these risks are mitigated by close clinical monitoring during the bed rest intervention (VTE prevention and glycemic control plans) and completion of the exercise recovery program. The participants will be informed that they may abort the study at any time. There are no alternative procedures/methods available with less risk or cost that provide comparable information to that obtained by the procedures described in this proposal.

Enoxaparin. There is a risk of bleeding, nausea, diarrhea, fever, swelling of the hands or feet, and injection site reactions including swelling, pain, bruising, and redness. Concomitant medications with known contraindication or interaction with low-molecular weight heparin (including anti-platelet agents, non-steroidal anti-inflammatory drugs) will be exclusionary.

RMR/RQ. There is no physical risk associated with RMR/RQ. Other risks include a feeling of claustrophobia experienced by some subjects while under the transparent “hood”.

Magnetic Resonance Imaging and Spectroscopy. There are no known biological risks associated with magnetic resonance imaging and spectroscopy. Some short-term discomfort may be experienced. The short-term risks associated with MRI are minimal, but include heating, loud noises and claustrophobia. There are some people who should not undergo MRI; the contraindication is largely based on the presence of metal objects within a person (i.e. pacemaker, aneurysm clip, metal fragments, etc.).

Hyperinsulinemic-euglycemic clamp. There is a risk of hypoglycemia (low blood sugar) during the clamp.

Mitigation of Risks

Blood draws and/or IV (lab samples, e.g.). All venipuncture will be conducted by qualified staff using aseptic techniques. Total blood volume throughout the entire study will be approximately 550 mls.

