Participants will be assigned unique identifiers for study-related records. All precautions will be taken to make sure that only authorized individuals will access participant research records. The collection of sensitive information about participants will be limited to minimum necessary to achieve the aims of the research, so that no unneeded sensitive information will be collected.

Early Withdrawal of Subjects

Investigator Withdrawal of Subjects

The participation in this study may be stopped at any time by the study PI without the participant's consent because:

- The study Medical investigator thinks it necessary for subject's health or safety;
- Participant has not followed study instructions;
- The TRI has stopped the study; or
- Administrative reasons require the participant's withdrawal.

Subject Request for Withdrawal from Study

Participation in this study is voluntary. Participants may decide not to participate in this study or may withdraw from this study at any time without penalty or loss of benefits.

Data Collection and Follow-up for Withdrawn Subjects

Participants who request withdrawal or who are withdrawn by the PI from the study will have their data maintained in the research database. This data and biospecimens from the withdrawn participant may be included in subsequent analysis. Participant withdrawal of biospecimens is not an option.

Adverse Event Reporting

Adverse Events

An adverse event (AE) is defined as both an expected side effect that is of a serious nature, or an unexpected side effect/event regardless of severity. Each participant is evaluated for adverse events at every study visit. Any event that is reported to the study staff and which meets the criteria of an adverse event will be documented as such and graded as to its attribution (unrelated to protocol, or possibly, probably, or definitely related to protocol) and severity (mild, moderate, or severe).

Recording of Adverse Events

At each contact with the subject, the investigator will seek information on adverse events by specific questioning and, as appropriate, by examination. Information on all adverse events will be recorded immediately in the source document, and also in the appropriate adverse event module of the case report form (CRF). All clearly related signs, symptoms, and abnormal diagnostic procedures results will be recorded in the source document.

Notification of Adverse Events

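### Read literally, the adverse event definition keeps expected non-serious events out of the AE module and so out of the AE rates that the safety reports must judge

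*Protocol*

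**What the plan says.** In the protocol's Adverse Event Reporting section, an AE is "defined as both an expected side effect that is of a serious nature, or an unexpected side effect/event regardless of severity". The same paragraph uses the definition as a filter: "Any event that is reported to the study staff and which meets the criteria of an adverse event will be documented as such", and such events are then graded for attribution and for severity (mild, moderate or severe). Under Recording of Adverse Events, the protocol adds: "Information on all adverse events will be recorded immediately in the source document, and also in the appropriate adverse event module". That module belongs to the case report form. Notification is left to the institution's IRB guidelines.

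The Potential Risks section lists many foreseen harms that are usually minor. For enoxaparin these include "injection site reactions including swelling, pain, bruising, and redness". For muscle biopsy they include bruising and haematoma, and also: "Local sensory loss may occur by cutting a subcutaneous sensory nerve (<1 in 100), which is almost always temporary". For blood draws and the oral glucose tolerance test, the list of harms ends with a remark about serious AEs: "infection at the blood draw site or IV insertion site (low risk of serious AEs" and "infection due to venipuncture (low risk of serious AEs".

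The Safety Monitoring and Monitoring Plan sections require the annual and DSMB reports to address whether AE rates agree with pre-study assumptions. The DSMB section assigns a physician to follow AE and SAE rates and the balance between groups.

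**The concern.** The definition has one branch for expected events, which requires seriousness, and one for unexpected events, which does not. Nothing covers an event that is expected and not serious. Because the definition also decides what is graded and entered in the AE module, the gap carries through to every summary built from that module.

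Participants undergo ten days of bed rest, enoxaparin injections, five muscle biopsies and insulin clamps, and half of them a supervised exercise programme. The protocol foresees many minor harms from these procedures. If staff follow the text, the AE tables will understate them. If some staff follow the text and others a broader habit, the tables will be inconsistent. In either case the comparison with pre-study assumptions cannot be made for the harms left out.

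**Working it through.** **1. The definition as a two-by-two.**

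| | Serious | Not serious |
|---|---|---|
| Expected | AE | not an AE |
| Unexpected | AE | AE |

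One of the four cells drops out. It follows that a mild or moderate non-serious AE can only be an unexpected one, although the severity scale is written for AEs in general.

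**2. Does anything put that cell back into the AE module?** Four provisions come close:

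- Related signs and symptoms are recorded, but only the source document is named (Recording of Adverse Events).
- Coordinators are told to make the principal investigator aware of all events, expected or not (Monitoring Plan). The text does not make these events AEs or send them to the module.
- Skin is checked twice daily during bed rest (Mitigation of Risks). No link to the AE module is stated.
- Individual cases are reviewed weekly (Data and Safety Monitoring Plan). This review covers AEs, so it inherits the definition.

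None restores the cell to the module or the rates.

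**3. How much of the risk section is touched?** Potential Risks has 12 procedure headings. All but DEXA name at least one effect that can occur in non-serious form: 12 − 1 = 11. For three of these (activity monitors, resting metabolic rate, MRI) the effects are only discomfort or irritation, which leaves 11 − 3 = 8. This counts headings, not events.

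**4. Which stated rates are affected?** The protocol gives five numerical event rates. Three are under Potential Risks: sensory loss below 1 in 100; biopsy bleeding needing hospital admission below 1 in 1000; heart attack, stroke or death with exercise testing below 0.01%. Two are in the venous thromboembolism text under Mitigation of Risks: baseline bleeding of 0.4%, and heparin-induced thrombocytopenia below 0.1%. Four of the five concern events that would ordinarily be serious and so stay captured. Only sensory loss falls in the missing cell.

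**5. Expected sensory-loss cases at the ceiling rate of 0.01.** Inputs:

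- 40 participants: 20 starters in each of two groups (Randomization).
- 30 participants: 15 completers (Sample Size Determination), assumed to be per group, times two.
- 5 muscle biopsies each: one after bed rest and four in recovery.

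The protocol does not say whether the rate is per person or per biopsy, so both are shown.

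- Per participant: 30 × 0.01 = 0.30 to 40 × 0.01 = 0.40.
- Per biopsy: 30 × 5 × 0.01 = 1.5 to 40 × 5 × 0.01 = 2.0.

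These are upper values, since the rate is stated as below 1 in 100. No rate is given for the other minor harms, so their number cannot be estimated from the protocol.

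**6. How the protocol uses the term elsewhere.** The remark about serious AEs after the lists for blood draws and the glucose tolerance test reads most naturally if the non-serious occurrences are AEs too. The DSMB text also treats AEs and SAEs as separate categories. Under the definition, that separation has no meaning for expected events, because an expected event is an AE only when it is serious.

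**The case against.** The strongest reply is that the wording is garbled, joining *both* with *or*, and that practice may be wider than the text. *Expected* and *serious* are not defined, so treating the listed risks as expected is an inference. This stands as a limit on how firmly the omission can be asserted. It is also a reason to clarify, since the undefined terms decide what is recorded.

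A reader might infer that the risk section flatly contradicts the definition. It does not. A remark that serious AEs are unlikely is compatible with a rule under which a listed risk becomes an AE once it is serious. The wider meaning is suggested, not stated.

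A reader might also infer that the gap distorts the comparison between arms. Bed rest, enoxaparin, clamps and muscle biopsies follow the same schedule in both arms, so most of the loss is non-differential. Only minor events tied to the exercise programme could fall mainly in one arm.

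Finally, the Phase IV schedule might suggest that the control arm is asked about AEs at far fewer visits, because most marks in its AE row carry the symbol for "only on this visit for exercise cohort". The protocol does not support that conclusion. Its AE section says that participants are evaluated at every study visit and that AE information is sought at each contact. Other rows of the same table place control participants at further visits, including 12 to 15, and the table's marks are damaged in the extracted text. More contact in a supervised exercise arm is also inherent in the design.

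**Conclusion.** The definition is wrong as written: taken literally, it keeps expected non-serious events out of the AE module and out of the AE rates that the annual and DSMB reports must judge. The point is minor. Serious events and all unexpected events are still captured. Source notes and the instruction to inform the principal investigator reduce the harm, so these events need not be lost altogether. The only stated rate affected is sensory loss, at 0.3 to 0.4 expected cases per-participant or 1.5 to 2.0 per-biopsy, both at the ceiling and for 30 to 40 participants. The primary outcomes are unaffected.

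The conclusion assumes that risks listed in the protocol count as expected and that staff apply the definition as worded.

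**What to change.** Define an AE as any untoward medical occurrence, regardless of expectedness or seriousness. Define *serious* and *expected*; *expected* could, for example, refer to the harms listed under Potential Risks. Enter every AE in the AE module and classify it by seriousness, severity, expectedness and attribution. Leave notification to the IRB guidelines, as the protocol already does, so that wider recording does not by itself change what is reported outside the study team.

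The cost is one rewritten definition, two added ones, and more AE form entries. No visit or procedure is added.
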